### **1.1 *Introduction***

Major depression (MDD) is a cause of disability worldwide, but the etiology of MDD remains unclear. An emerging concept is that inflammation may have relevance, especially in MDD. We have data supporting increased inflammatory cytokines in MDD compared with controls that are associated with decreased hippocampus and amygdala volumes. MDD also had impairment in neuropsychological function in episodic memory, executive function, decreased hippocampus and amygdala resting state functional connectivity. Antidepressant treatment improved IL-6 levels, neuropsychological testing and resting state connectivity.

We will recruit patients with MDD (n = 100) and controls (n = 50) to characterize immune function, brain structure and connectivity and neuropsychological function. Using the Hospital of University of Pennsylvania's Pepper Lab we will measure participants' c-reactive protein (CRP) levels, and stratify participants according to CRP level (i.e. high (CRP  $\geq$ 3) and low (CRP  $<$ 3)). All participants with MDD (n=100), will receive a selective serotonin reuptake inhibitor (SSRI) antidepressant and we will randomize them to SSRI plus placebo (n $\leq$ 50) or SSRI + celecoxib (n $\leq$ 50). We will assess participants pre- and post-treatment with peripheral and central cytokine levels, neuropsychological tests and brain resting state functional connectivity.

Hypothesis 1: a) Compared with matched controls, MDD will have abnormalities in peripheral and inflammatory cytokines, neuropsychological function, hippocampal, amygdala and prefrontal cortex (PFC) structure and functional connectivity; b) Peripheral/central inflammatory cytokine levels will be associated with volume loss in hippocampus and amygdala; and c) Cumulative duration of depression will correlate with volume loss in hippocampus, amygdala, and PFC. d) Across the lifespan there will be an age effect interaction with depression.

Hypothesis 2: a) Once subjects have completed the antidepressant treatment, they will have greater normalization of IL-6 and IL-10, greater improvements in memory, executive function, and in resting state functional connectivity compared to their baseline measures; b) Improvement in clinical depressive scores will correlate with normalization of inflammatory cytokines; c) Those randomized to the addition of celecoxib (vs placebo) will have additive improvements in cytokines, resting state functional connectivity and depression scores.

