A meta-analysis of five (2) post-approval clinical trials associated lower depression scores with celecoxib treatment, 200 mg qd over 6 weeks, in patients with active osteoarthritis, n=607, compared to patients exposed to placebo (2). These clinical trials were highly protected against bias by following a multicenter, randomized, double-blinded, placebo-controlled, active-comparator, parallel-group design (2). The authors write that a significant increase in systolic or diastolic blood pressure and heart rate was not evident after 6 weeks of celecoxib treatment (2). This supports a good safety profile for this celecoxib dosing regimen, in particular, when considering that 48% of patients (291/607) had hypertension at baseline, 20% (121/607) hyperlipidemia, and 17% (103/607) diabetes mellitus as baseline conditions. The high morbidity is also reflected in that 51% (310/607) of patients report at baseline to receive pharmacotherapy to treat cardiovascular disease (2). CRP levels have been shown to highly correlate with cytokine levels. Validation of commercially available methods of CRP has been conducted and shown that semi-quantitative CRP strips can distinguish between normal and high levels of CRP within individuals very simply (3).

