**2.2 Study Design**

100 depressed and 50 control subjects, age 18-80, male and female, will be recruited for this study. Depressed participants will be stratified based on their c-reactive protein (CRP) levels (i.e., “High” CRP $\geq$ 3 and “Low” CRP<3). All participants will be started on either 10 mg of escitalopram + placebo or 10 mg of escitalopram + celecoxib (400mg/day) daily for 3 days. Following this lead-in dose of the SSRI they will then take 20 mg daily thereafter for 39 days and have no changes in their dose of placebo or celecoxib. Follow-up visits for all depressed participants will occur at 1 week, 2-weeks, and 4-weeks, following the start of treatment. The study coordinator and PI will monitor side effects and vital signs, and the PI may adjust the medication dosage depending on the patient's response to treatment and/or the presence of side effects. Final dose (10 mg versus 20 mg, or a dose between 10 mg and 20 mg, e.g., 15 mg) will be determined by clinical response and side effects. This decision will be based on an ongoing discussion between the participant and the study doctor. Participants who remit will have their end of study visit with a blood draw, and neuropsych testing at 6 weeks. Participants will then taper off medication at 10 mg for 3 days (if taking 20 mg during study). Based on past studies, less than 10% of participants will be taking less than 20 mg/day of SSRI at the end of the study.

Participants initially randomized to escitalopram + placebo, who do not remit will be treated with 6 weeks of escitalopram + celecoxib. They will not repeat the baseline visit, but will re-complete medication visits at week 1,2, and 4, After the 6 weeks of escitalopram + celecoxib they will undergo a 3rd MRI, neurocognitive session, and blood draw. Those who complete the study at this point will taper off medication at 10 mg for 3 days.

CONFIDENTIAL

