### **2.5 Target population**

One-hundred depressed subjects, aged 18-80, right handed, male and female (50 with high-CRP levels ( $CRP \geq 3$ ) and 50 with low-CRP levels ( $CRP < 3$ )). In addition, 50 non-depressed controls, matched on demographic and vascular risk factors.

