## **6 Analysis Plan**

### **6.1 Data Analysis and Predictions**

At a basic level, the design of this trial is simple repeated measures design with a) two replicates (time points) b) baseline covariates and outcomes, and c) a single between-person factor (initial case-control depression status). The data collected at two time points to be included in analysis (pre- and post-treatment) will be the depression severity, inflammatory markers, resting state functional connectivity and neuropsychometric data. There have been no published studies to date examining adjuvant celecoxib and SSRI treatment in patients who simultaneously received assessment of inflammatory biomarkers. However, based on our own small pilot sample we will have greater than 85% power to detect differences in changes in IL-6 between SSRI responders and SSRI + celecoxib responders. Volumetric data and confounders to be included in the analysis will be collected at baseline. Classic models of change scores can be used where the baseline level can be controlled giving the so-called residual change score. Use of residualized change scores has several analytic advantages: (1) control for variance (the best predictor of today's value is yesterday's value), (2) statistically each subject is started at the same point. Thus, our estimation model will be extended from the classic model of change scores to a repeated measures ANOVA (analysis of variance) or mixed model repeated measures design. A joint modeling approach with mixed models for repeated measures data can be used to address within-subject variation and between-subject variation of the repeated measurements of multiple

CONFIDENTIAL

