Aim 2: Characterize the reversibility of brain dysfunction, including cognitive impairment with treatment of depression and its association with inflammation. Hypothesis 2a: Subjects randomized to treatment will have greater normalization of IL-6 and IL-10, greater improvements in memory, executive function and improvements in resting state functional connectivity compared to those randomized to placebo. For an unadjusted analysis, a paired t-test can be used to determine if there is a difference in the pre-treatment and post-treatment inflammatory cytokines. Mixed models will be utilized to assess if the inflammatory markers change over time adjusting for confounders. A mediator analysis will be utilized to determine whether MADRS has an effect independent of treatment on the inflammatory levels. The first

CONFIDENTIAL

approach would be to test for an interaction effect between baseline MADRS and treatment in a mixed model with inflammatory markers as the outcome adjusting for MADRS, treatment, and an interaction between MADRS and treatment. If the interaction term is not significant we will determine if MADRS independently of treatment or additively with treatment is related to inflammatory markers. Structural equation models can be an alternative approach for the mediator analysis.

Hypothesis 2b: Improvement in clinical depressive scores post treatment will be correlated with changes in cytokine levels. Change score models or joint mixed models will be utilized to assess the relationship between depression scores (outcome) and inflammatory markers, while adjusting for confounders in the depressed subjects.

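### CRP stratum defines the depressed cohort, but no Aim 2 model adjusts for it or prespecifies an arm-by-CRP estimate

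*Combined protocol and SAP*

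**What the plan says.** Section 2.2 states: "Depressed participants will be stratified based on their c-reactive protein (CRP) levels", with the cut at 3. Sections 1.1, 5.2 and 5.4 repeat this. Section 2.5 sets the mix of the 100 depressed participants at "50 with high-CRP levels" and "50 with low-CRP levels". Section 1.2 gives the link to the outcome: "CRP levels have been shown to highly correlate with cytokine levels".

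The Aim 2 hypotheses concern change in cytokines. Section 6.3 has Hypothesis 2a as "Subjects randomized to treatment will have greater normalization of IL-6 and IL-10". Hypothesis 2c in Section 1.1 reads "Those randomized to the addition of celecoxib (vs placebo) will have additive improvements in cytokines".

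Section 6 does not use the stratum. Section 6.1 describes the design as having "a single between-person factor (initial case-control depression status"). It gives age, race, education, statin use and gender as examples of confounders, and it plans a sensitivity analysis by statin and ARB use. For Aim 2, Section 6.3 says: "Mixed models will be utilized to assess if the inflammatory markers change over time adjusting for confounders". It names one modifier of treatment, baseline MADRS. The Hypothesis 2a power paragraph in Section 2.7 treats the 100 depressed participants as one pool.

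**The concern.** CRP is the only variable by which the depressed cohort is said to be stratified, and its mix is fixed by quota. Two things follow when the analysis leaves it out.

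First, a baseline variable that the protocol itself says is highly correlated with the outcome is left out of the arm comparison, where adjusting for it would ordinarily add precision.

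Second, if the arm effect differs by CRP, the pooled estimate is an average whose weights come from the 50:50 quota, and the plan has no prespecified way to show this. A null pooled IL-6 result could not then be told apart from an effect present mainly in high-CRP patients. A CRP analysis added after unblinding would be read as a post hoc subgroup.

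**Working it through.** **Inputs, all from Section 2.7 (Hypothesis 2a, IL-6) unless stated.** Two-tailed t-test at 5%; SD 3.6; 50 per group; detectable difference 2.1; preliminary difference 2.7. The 10% attrition figure is given there for the connectivity calculation. The 50/50 CRP mix is from Section 2.5.

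**1. The plan's own figure.** The standardized difference is 2.1/3.6 = 0.583. A two-sample t-test needs 47.1, so 48 per group, for 80% power. At 50 per group power is 82.3%, and at 45 per group (10% attrition) it is 78.1%. The stated 80% is reproduced closely enough, for a single pool.

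**2. Pooled power if the effect differs by CRP.** Let f be the low-CRP effect as a fraction of the high-CRP effect D. The documents do not give f, so it is varied. With half the cohort in each stratum:

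pooled difference = D × (1 + f)/2, with SD held at 3.6.

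| f | Pooled difference, D = 2.7 | Power, 50 v 50 | Pooled difference, D = 2.1 | Power, 50 v 50 |
|---|---|---|---|---|
| 0 | 1.35 | 46% | 1.05 | 30% |
| 0.25 | 1.69 | 64% | 1.31 | 44% |
| 0.50 | 2.03 | 80% | 1.58 | 58% |
| 0.75 | 2.36 | 90% | 1.84 | 72% |
| 1 | 2.70 | 96% | 2.10 | 82% |

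**3. High-CRP stratum alone.** With 25 v 25, which assumes that the arms balance within stratum, power is 74% for 2.7 and 52% for 2.1.

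**4. Where pooled and stratum-only tests are equal.** Setting the two noncentrality parameters equal gives (1 + f)/2 × √(50/2) = √(25/2). So (1 + f)/2 = 3.536/5 = 0.707, and f = 0.41. Above about 41% the pooled test is the stronger one.

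**5. Arm-by-CRP interaction.** With 25 per cell, SE = 3.6 × √(4/25) = 1.44. If the low-CRP effect is zero and D = 2.7, the ratio is 2.7/1.44 = 1.875 and power is about 46%. For 80% power the two stratum effects would have to differ by about (1.96 + 0.84) × 1.44 = 4.03.

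**6. Do the general clauses in Section 6.1 bring CRP in?** The confounder rule adjusts for a variable related both to the outcome and to the covariate of interest. In a randomized comparison CRP is unrelated to arm in expectation, so the rule gives no reliable reason to select it. The clause on known covariates and their interactions does not name CRP, and it judges models by the change in the estimate and by p-values, which is not prespecification. Controlling for the baseline level of the outcome is permitted. That adjusts for starting value but does not estimate whether the arm effect differs by CRP.

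**The case against.** A reader might infer something stronger: that the low-CRP half has little to normalize, that the trial's premise places the effect in inflamed patients, and that the normalization conclusion should therefore come from the CRP ≥3 stratum. The documents do not support this.

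- They give no IL-6 or IL-10 values by CRP stratum and no coefficient for the asserted correlation. The cut of 3 is a CRP cut, not a cytokine cut. For IL-10, where Section 6.3 predicts that low values go with smaller volumes, nothing says that CRP <3 implies a normal level.
- The hypotheses are stated for MDD as a whole, and low-CRP patients are enrolled by design.
- The 2.7 is a pilot difference between nonmedicated and medicated groups, whereas both arms here receive escitalopram. The pilot's CRP mix is not stated, so 2.7 may already contain some dilution. The 46% v 74% contrast also needs a low-CRP effect of exactly zero.
- A stratum-based conclusion would need a decision rule and multiplicity control that the plan lacks, and 25 per arm would still leave a null result ambiguous.

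Two narrower points also stand. The single-factor sentence in Section 6.1 omits treatment arm as well as CRP, and Section 6.3 does name treatment, so that sentence alone does not prove a gap specific to CRP. Adding CRP is not forbidden, and controlling baseline IL-6 may already absorb much of a CRP main effect in the IL-6 model.

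None of this puts the stratum or an arm-by-CRP estimate into the plan.

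**Conclusion.** The concern holds as an omission. CRP shapes the depressed cohort, yet Section 6 prespecifies neither adjustment for the stratum nor an arm-by-CRP estimate for Aim 2. Effect dilution can be neither excluded nor assessed as planned.

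The size is conditional. With a high-CRP effect of 2.7, pooled power lies between 46% and 96% depending on an unknown f, and it stays at about 80% or more once the low-CRP effect is half the high-CRP effect. These figures rest on a common SD of 3.6, full retention, an even CRP split, arms balanced within stratum (no section says that randomization itself is stratified by CRP), and a pilot difference from a different contrast.

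They illustrate why the estimate should be prespecified. They do not show that the pooled test is underpowered, and they do not justify replacing it with a high-CRP subgroup conclusion.

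**What to change.** In Sections 6.1 and 6.3:

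1. Enter the screening CRP stratum (≥3 v <3) as a fixed factor, together with the baseline value of the outcome, in every Aim 2 model that compares arms in depressed participants.
2. Prespecify arm × CRP stratum (arm × CRP × time in the repeated-measures form) for IL-6 and MADRS as a secondary or exploratory analysis. Report between-arm estimates within each stratum with confidence intervals, and say that the interaction is not a decisive test.
3. State that the pooled between-arm estimate remains the basis for the conclusions on Hypotheses 2a and 2c.

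The cost is wording only, because CRP is already measured on everyone at screening. The models spend one or two degrees of freedom, and the interaction estimate will be imprecise at about 25 per cell. The change should be made before unblinding.

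### Section 6.3 words Hypothesis 2a as a comparison with placebo but gives the cytokines only pre-post tests; Hypothesis 2c is not carried into 6.3, and no arm comparison is stated for MADRS

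*Combined protocol and SAP*

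**What the plan says.** **The design.** Section 1.1 states: "All participants with MDD (n=100), will receive a selective serotonin reuptake inhibitor (SSRI) antidepressant and we will randomize them to SSRI plus placebo" or SSRI plus celecoxib, with up to 50 in each arm. Escitalopram is common to both arms, and only celecoxib versus placebo is randomised.

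**The hypotheses.** Section 1.1 words Hypothesis 2a within person: after treatment, participants will show "greater improvements in memory, executive function, and in resting state functional connectivity compared to their baseline measures". It puts the randomised claim in Hypothesis 2c: "Those randomized to the addition of celecoxib (vs placebo) will have additive improvements in cytokines, resting state functional connectivity and depression scores". Section 6.3 words 2a between arms, with greater cytokine normalisation, better memory and executive function, and "improvements in resting state functional connectivity compared to those randomized to placebo".

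**The tests.** For 2a, section 6.3 says that in an unadjusted analysis "a paired t-test can be used to determine if there is a difference in the pre-treatment and post-treatment inflammatory cytokines", and then: "Mixed models will be utilized to assess if the inflammatory markers change over time adjusting for confounders". Treatment appears once in 6.3 as a model term. That is in the mediator analysis, a mixed model for the markers "adjusting for MADRS, treatment, and an interaction between MADRS and treatment", where the term tested is baseline MADRS by treatment. Section 6.1 offers a general family (baseline-controlled change, repeated measures ANOVA, mixed model) and names case-control depression status as the one between-person factor. Hypothesis 2c does not appear in 6.3.

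**MADRS.** Sections 2.1 and 6.2 define treatment response as the post-treatment score adjusted for baseline, and section 5.3 makes MADRS the primary measure of depression severity. None of these sections compares arms.

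**Section 2.7.** IL-6 under Hypothesis 2a is sized on a two-tailed t-test of 50 against 50. A treatment group by time test is committed to for functional connectivity only.

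**The concern.** The randomisation exists to isolate what celecoxib adds to escitalopram. Section 1.1 reports from the investigators' own data: "Antidepressant treatment improved IL-6 levels, neuropsychological testing and resting state connectivity". A fall in IL-6 from baseline to week 6 is therefore to be expected in both arms even if celecoxib does nothing.

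Followed as written, section 6.3 answers whether markers change during treatment. It does not answer whether they change more with celecoxib than with placebo, which is what 6.3's own wording of 2a and section 1.1's Hypothesis 2c ask. For MADRS there is no stated estimate of the celecoxib effect at all. The model, the analysis set and the time window for the randomised comparison would then be chosen after the data are in. The window matters because placebo-arm participants who do not remit move to open-label celecoxib after week 6 (section 2.2), so an undefined post-treatment value could mix the arms.

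**Working it through.** **1. Reproduce the plan's IL-6 figure.** Inputs from section 2.7: difference 2.1, SD 3.6, 50 per group, two-sided 5%, 80% power.

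- Required n per arm = 2(z₀.₉₇₅ + z₀.₈₀)²(SD/difference)² = 2 × (1.960 + 0.842)² × (3.6/2.1)² = 2 × 7.85 × 2.94 = 46.1, so 47.
- With 50 per arm: 2.1 / (3.6 × √(2/50)) = 2.92; 2.92 − 1.96 = 0.96; power 83% (normal) or 82% (t). The difference detectable at 80% power is 2.04.
- With 10% attrition, the rate 2.7 uses for connectivity, 50 × 0.9 = 45 per arm and power is 79% (normal) or 78% (t).

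So 2.1 is a slightly conservative two-sample figure. Section 2.7 sized IL-6 on a between-group test, whereas 6.3 assigns a within-person one.

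**2. What each test estimates.** Let e be the mean change with escitalopram plus placebo, and c the extra change from celecoxib.

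| Analysis | Estimates |
|---|---|
| Paired test, equal arms pooled | e + c/2 |
| Paired test, celecoxib arm only | e + c |
| Difference in change between arms | c |

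With c = 0, both paired tests still estimate e. Only the third row isolates celecoxib.

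**3. Where an arm test is stated.**

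| Outcome | Section 6.3 | Elsewhere |
|---|---|---|
| IL-6 | Paired test; change over time | Two-sample sizing in 2.7; power statements in 6.1 with no model term |
| IL-10 | Paired test; change over time, as an inflammatory marker | None |
| Connectivity | No method given under 2a | Group by time in 2.7 |
| Memory, executive function | No method given under 2a | Generic model family in 6.1 |
| MADRS | Related to cytokines in 2b; covariate in the mediator model | Defined in 2.1 and 6.2; no arm comparison |

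**4. The power statements in 6.1.** One claims more than 85% power for IL-6 among responders, a subset formed after randomisation. The other claims more than 95% from randomising 53 subjects in a Phase II. Neither describes the up to 100 randomised at baseline, and neither can be reproduced, because the effect sizes are not in the documents. As a guide, 95% power with 26 against 27 needs a standardised difference of about 1.01. The section 2.7 values give 55% (2.1/3.6) or 76% (2.7/3.6) with 53 subjects.

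**5. Power of the arm test proposed below.** Assume a celecoxib effect of 2.1. Section 2.7 attaches that figure to medicated versus nonmedicated groups, which this design does not have. If 3.6 is the SD of change, power is 82% at 50 per arm and 78% at 45. If 3.6 is a single-visit SD, the effective SD is 3.6√(2(1 − r)) for arm by time and 3.6√(1 − r²) with baseline adjustment, where r is the assumed baseline to week-6 correlation. At 45 per arm:

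| r | Arm by time | Baseline-adjusted |
|---|---|---|
| 0.3 | 64% | 82% |
| 0.5 | 78% | 88% |
| 0.7 | 94% | 97% |

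No such figure can be given for MADRS, for which the documents supply neither effect size nor SD.

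**The case against.** **The paired test fits one wording of 2a.** Section 1.1 defines 2a as change from baseline, and Aim 2 is about reversibility with treatment. Under that wording a paired test is right. This stands, and it confines the mismatch to 6.3's between-arm wording. It does not help 2c, which then has no stated test for cytokines or depression scores.

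**The plan has between-arm tests elsewhere.** A reader might infer that the document contains none. That is not supported: section 2.7 commits to group by time for connectivity and sizes IL-6 on a two-sample test. Connectivity therefore needs only a cross-reference. For IL-6, 2.7 implies a comparison that 6.3 does not carry out.

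**The pre-post tests cover markers only.** A reader might also infer that 6.3 applies them to every outcome. It does not. For cognition, connectivity and MADRS there is no pre-post test to replace, and what is missing is a stated arm test in 6.3.

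**The language is permissive and treatment is in one model.** The paired test is offered as an unadjusted option, 6.1 describes its single factor as a basic view of the design, and the mediator model contains treatment. All true. But the plan does not say the treatment coefficient will be tested, and no treatment by time term is named for the markers.

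**False positives.** The strongest reading would be that a pre-post fall will be declared a celecoxib effect. Section 6.3 does not say so. Only under that reading, with an assumed equal change of 0.1 to 0.5 SD of the change score in both arms, would a pooled paired test (n = 90) be significant in about 16% to over 99% of trials, and a celecoxib-arm test (n = 45) in about 10% to 91%, against 5% for an arm comparison. The documents give no IL-6 change on escitalopram alone, so these rates are an aside.

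**Conclusion.** The point holds for 6.3's wording of 2a as it concerns the inflammatory markers, and for Hypothesis 2c as it concerns cytokines and MADRS. Section 6.3 states a between-arm claim and supplies within-person tests, 2c is dropped, and MADRS has no arm comparison anywhere in the documents. For IL-6, sections 2.7 and 6.3 conflict. For connectivity, a suitable test exists but sits in the sample-size section.

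The size is best stated as a count: IL-6, IL-10 and MADRS have no specified arm test in Section 6. No error rate follows from the text. The conclusion rests on two facts in section 1.1, that both arms take escitalopram and that only the celecoxib addition is randomised. It needs no assumption about effect sizes. It should be corrected before analysis, because as written 6.3 cannot answer the randomised question.

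**What to change.** 1. Reconcile the wording of Hypothesis 2a across sections 1.1, 2.7 and 6.3, including the medicated and nonmedicated labels in 2.7.
2. Add Hypothesis 2c to section 6.3. For IL-6, IL-10 and MADRS (and for memory and executive function if 2a stays between-arm), specify, for example: week-6 value regressed on randomised arm and baseline value, or arm by time in a mixed model, in all randomised depressed participants as randomised, using week 0 to 6 data before the open-label phase.
3. Carry the connectivity group by time test from section 2.7 into 6.3.
4. List randomised arm as a between-person factor for Aim 2 in section 6.1.
5. Keep the paired cytokine test only as a description of within-person change.

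The cost is SAP wording and slightly more analysis work. No new data or visits are needed.
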